5.1.4.1. Overall Conclusions

Collectively, the findings in the continuous 3- and 6-month daily-dosing toxicity studies, particularly the degeneration of the large blood vessels, imply that long-term, daily dosing of LY2157299 may carry a risk in patients for developing aneurysms. Reversibility was not assessed in the 3- or 6-month toxicity studies, but in a non-GLP reversibility study in rat, data indicate the cardiovascular lesions are partially reversible, but those that are still present following the recovery period are still adverse. The intermittent-dosing regimen in patients is based on the safety demonstrated in the rat and dog following 1 month of continuous daily dosing in which the NOEL for any effects in the heart was 150 and 20 mg/kg in the rat and dog, respectively, and a 3-month intermittent-dosing study in the rat in which the NOEL for any effects in the heart was 50 mg/kg (see [Table JBAK.2](#) for margin-of-safety [MOS] calculations). Although the likelihood of occurrence or the extent and timing of such a risk observed after daily

dosing is not known in humans, LY2157299 will be administered as an intermittent-dosing regimen in this patient population which has a poor prognosis and rapidly advancing cancer.

Table JBAK.2. Margin of Safety Based on NOEL to Cardiovascular Effects

Clinical Dose (mg/day)		160	300
Measured AUC _{0-24hr} (µg•hr/mL) at steady state BID		2.2	4.3
Simulated AUC _{0-24 hr} (µg•hr/mL) at steady state QD ^a		4.1	7.7
Rat NOEL^b (150 mg/kg) (30 days; daily dosing)			
AUC _{0-24 h} (µg•hr/mL) ^c	36.3	Measured (Steady State BID)	16.5 8.4
		Simulated ^a (Steady State QD)	8.9 4.7
Rat NOEL^b (50 mg/kg) (3-months intermittent; 2 weeks on/2 weeks off)			
AUC _{0-24 h} (µg•hr/mL) ^c	8.0	Measured (Steady State BID)	3.6 1.9
		Simulated ^a (Steady State QD)	2.0 1.0
Rat LOEL (150 mg/kg) (3-months intermittent; 2 weeks on/2 weeks off)			
AUC _{0-24 h} (µg•hr/mL) ^c	24.2	Measured (Steady State BID)	11 5.6
		Simulated ^a (Steady State QD)	5.9 3.1
Dog NOEL^b (20 mg/kg) (30 days; daily dosing)			
AUC _{0-24 h} (µg•hr/mL) ^d	23.9	Measured (Steady State BID)	10.9 5.6
		Simulated ^a (Steady State QD)	5.8 3.1

Margin of safety based on NOEL to cardiovascular effects in 30 day daily and 3-month intermittent dosing GLP toxicology studies in rat and dog and measured clinical AUC (shaded row indicates the relevant MOS for LY2157299) or exposure multiple to an effect dose (LOEL) for cardiac lesions in the rat in a 3-month intermittent dosing GLP toxicology study.

Abbreviations: AUC = area under the concentration curve; BID = twice daily; GLP = good laboratory practice; LOEL = lowest-observed-effect level; MOS = margin of safety; NOEL = no-observed-effect level; QD = daily.

^a Simulations based on all clinical data from Study JBAH (Cohorts 1 to 5) assuming QD dosing.

^b NOEL is based on absence of any cardiovascular changes at this dose.

^c AUC from males were used to calculate MOS or exposure multiple to the LOEL.

^d AUC from males and females was averaged since no exposure differences were noted.

5.1.5. Clinical Experience

5.1.5.1. Safety

As of 15 September 2015, approximately 696 patients and 20 healthy subjects have received treatment with LY2157299, either in monotherapy or in combination with chemotherapy. These include clinical trial patients with advanced/metastatic cancer, solid tumors, glioblastoma, pancreatic cancer, HCC and myelodysplastic syndromes (MDS).

Overall, few SAEs deemed by investigators to be associated with drug treatment have been reported. Most treatment-related SAEs have been reported in 1 patient except anemia (2 patients

with HCC), cardiac failure (2 patients with MDS), neutropenia (1 patient with glioblastoma and 1 patient with HCC), thrombocytopenia (2 patients with glioblastoma), peritoneal hemorrhage (2 patients with HCC), and diarrhea (1 patient with glioblastoma and 1 patient with HCC). The SAE profile seems to differ when LY2157299 is used in patients with glioblastoma, MDS, and HCC, indicating a possibility that reporting rates are influenced by the underlying disease and there have been no trends or signals noted in the reported SAEs.

The most common TEAEs ($\geq 10\%$) for LY2157299 monotherapy are fatigue (19%), anemia (18%), abdominal pain (18%), edema peripheral (15%), nausea (15%), asthenia (14%), diarrhea (14%), vomiting (14%), abdominal pain (12%), headache (12%), constipation (10%), decreased appetite (10%), and pruritus (10%). Most of these AEs were of mild or moderate severity.

The addition of LY2157299 to standard cancer treatments appeared to have no effect on the established toxicity profile of these standard therapies.

Extensive cardiac safety monitoring has been conducted in all clinical studies, and available data has shown no indication of a LY2157299-related cardiac toxicity.

The intermittent dosing regimen of 14 days on treatment with LY2157299 followed by 14 days off treatment (1 cycle = 28 days) that has been used in clinical development to date appears to be well tolerated with no clinically significant valvulopathies or aneurysms reported or observed at dosages of up to 300 mg/day.

For additional details, please refer to the LY2157299 IB, Section 6.

5.1.5.2. JBAK: Brief Summary of Results to Date

At the time of Amendment (e), Part A and Part B of the study have completed. A total of 149 patients were enrolled (109 in Part A and 40 in Part B). Eighty-five percent of patients were male and the median age was 65 years. Fifty-six percent of patients had an ECOG performance status (PS) of 0 and 44% had a PS of 1. Eighty-six percent of patients had a Child-Pugh Class A score and 14% had a Class B score. Etiology of disease was as follows: hepatitis C 24%, hepatitis B 20%, alcohol 20%; multiple 9.4%. Overall, 83% of patients had received prior sorafenib. Eleven patients discontinued treatment due to AEs: 8 were considered related to study treatment. Grade 3/4 AEs possibly related to treatment were observed in 26 (17%) patients. Of these AEs, neutrophil count decrease was observed in 4 patients. Anemia, hypoalbuminemia, decreased bilirubin, fatigue and embolism were observed in 2 patients each. All other AEs occurred in just 1 patient. Median TTP was 11.9 weeks (95% CI: 6.3, 12.6) in Part A and 18.0 weeks (95% CI: 10.0, 24.0) in Part B. Median OS was 31.4 weeks (95% CI: 22.9, 40.6) in Part A and 73.0 weeks (95% CI: 45.4, 104.7) in Part B. The median OS for the overall population was estimated as 40.4 weeks (95% CI: 31.1, 52.4) (Giannelli et al. 2016).

Enrollment into Part C has completed and maturation of the data is awaited. Enrollment is ongoing in Part D of the study.

5.1.5.3. Rationale for the Study

The scientific justification of investigating LY2157299 in HCC is compelling based on the role of TGF- β in the process of fibrosis and cirrhosis leading to HCC. The evidence of antitumor effects in several models with TGF- β inhibitors, such as LY2109761 and LY364947, suggest that LY2157299 will have activity in HCC. Also, the relatively favorable toxicity profile differentiates LY2157299 from other kinase inhibitors with their characteristic cardiovascular and cutaneous toxicity. Therefore, it is anticipated that LY2157299 will:

- Increase immunocompetence in HCC patients
- Show increased antitumor activity due to a reduction in fibrogenesis, remodeling, neoangiogenesis, and invasiveness

In addition to the scientific rationale and the expected improvements, the study is justified because of the following reasons:

- LY2157299 has shown a favorable short- and long-term toxicity profile in Study JBAH.
- No indication of cardiac insufficiency.
- Three Grade 3 to 4 events (CTCAE v 3.0) (thrombocytopenia, thromboembolism, ischemic stroke) possibly related to study drug occurred in Study JBAH in patients who received LY2157299 treatment.
- Evidence of tumor responses while patients were treated with single-agent LY2157299 in Study JBAH, the study in GBM patients.
 - Two patients had complete responses (CRs) and 3 patients had partial responses (PRs). Three patients were treated for more than 20 cycles (updated information in the IB).
- Clinical exposures achieved in Study JBAH are 1.9-fold below a no-observed-effect level for cardiac toxicity in the rat (most sensitive species for cardiac effects) suggesting clinical activity can be achieved at exposures lower than those required to elicit toxicity in nonclinical species.

The proposed immunomodulatory as well as anti-invasive properties of LY2157299 suggest that a clinical investigation in the first-line setting of patients with HCC is promising. Hence, it may be acceptable to treat patients with LY2157299 even before they are considered to receive sorafenib or other antivasular agents.

In summary, the combination of a well-tolerated agent such as LY2157299 in a disease with high unmet medical need, justifies the evaluation of this agent in the first- and second-line treatment of HCC. Thus, the overall benefit/risk profile is acceptable in this setting.

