5.1.3. Clinical Pharmacokinetics of LY2157299

As of 19 August 2011, 39 patients have been treated with LY2157299 in an ongoing study, Study H9H-MC-JBAH (JBAH). Of 39 patients, noncompartmental PK analysis has been performed on 37 patients.

Results from all 5 cohorts showed rapid absorption of LY2157299, as demonstrated by measurable plasma concentrations at the first sampling time (0.5 to 2 hours). At steady state, on Day 14, the median time to maximum concentration ($t_{\text{max,ss}}$) ranged from 0.5 to 2 hours postdose, independent of dose. Both the maximum observed concentration at steady state ($C_{\text{max,ss}}$) and exposure increased with dose. The geometric mean of the apparent clearance at steady state (CL_{ss}/F) was similar across Cohorts 3, 4, and 5, whereas for the first 2 cohorts the scheduled sampling time was only up to 8 hours post dose and the parameter could not be estimated with any degree of certainty. No accumulation of LY2157299 in the 5 cohorts was

observed over the 14-day twice-daily (BID) dosing regimen, with accumulation ratio (RA) observed to be approximately 1. A population PK model, based on Cohorts 1 through 5 data, was developed. A first order absorption linear 2-compartment model, with elimination from the central compartment provided the best fit to the plasma data. The mean population clearance of LY2157299 was 38.4 L/h with standard error, expressed as a percentage coefficient of variation of 8% and the steady state volume of distribution (V_{ss}) was 193 L. From the population PK analysis of all 5 cohorts' data, the between-patient variance was estimated to be 46% on the population apparent clearance. The between-occasion variability on apparent CL was estimated at 18%.

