The dose-proportionality analysis was performed for the PK parameters area under the plasma concentration-time curve from 0 to infinity ($AUC[0-\infty]$) and $C_{max,ss}$ (Day 15) using results from 30 patients from all 5 cohorts (pooled across Cycles 1 and 2 for Cohorts 3, 4, and 5). From this analysis, there was no evidence of a difference between Cycles 1 and 2 for Cohorts 3, 4, and 5. The estimated ratios of geometric means for $AUC(0-\infty)$ and $C_{max,ss}$ between 150 mg BID and 20 mg BID were estimated as 7.90 (90% CI: 2.85, 22.0) and 3.56 (90% CI: 2.09, 6.06), respectively. For a doubling of dose, the fold increases for $AUC(0-\infty)$ and $C_{max,ss}$ are 2.04-fold with corresponding 90% confidence limits (1.43, 2.89) and 1.55-fold with 90% confidence limits (1.29, 1.86), respectively. Within- and between-patient coefficients of variation were estimated as 26% and 40% for $AUC(0-\infty)$ at steady state, respectively, and 34% and 56% for $C_{max,ss}$, pooled across the 5 cohorts from the dose-proportionality analysis.

For additional information see Section 6.1 in the IB.

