5.1.7. Rationale for Amendment (b)

The protocol is amended for the following reasons:

As part of the continuous monitoring of safety, PK, and laboratory markers in patients with HCC, the sponsor noted that patients are staying on study beyond 4 months. Furthermore, the 300 mg/day dose appears to have no evidence of increased toxicity. There appears to be no difference in the number of patients at the 160-mg/day and the 300-mg/day dose who stayed beyond 4 months. In addition, in all other ongoing trials with LY2157299, the dose of 300 mg/day was selected for future clinical development.

Preliminary PK data from the first interim analysis (n=20 patients) suggest that patients administered 300 mg/day have higher exposures than previously observed for the same dose level (Study JBAH) during the treatment period. LY2157299 appears to be fully eliminated after the 14-days off period of a cycle (additional PK sampling is added to study the clearance of LY2157299). The lowest exposure level (ie, most conservative) in the most sensitive nonclinical species administered LY2157299 in a clinically relevant dosing schedule (2 weeks on/2 weeks off) in which cardiac effects were observed was 24 $\mu\text{g}\cdot\text{hr}/\text{mL}$ (Table JBAK.2). The findings at this dose level (150 mg/kg) consisted of a single male rat (n=10/group) with minimal inflammation in the aortic valve and ascending aorta. Administration of 300 mg/day to patients with HCC may result in higher than anticipated exposures; however, due to the clinical safety profile observed thus far and the benefit:risk in this patient population, this approach is considered acceptable.

Because of these reasons and the lack of substantial evidence that the 160-mg/day dose is superior to the 300-mg/day dose, the dose of 300 mg/day is selected for the continuation of this trial.

For Part B, it was decided to evaluate the effects of LY2157299 in patients with AFP <1.5x upper limit of normal (ULN) to have an overall assessment of LY2157299 efficacy in all HCC patients. At the time of the decision to focus on the 300-mg/day dose, 74 patients were randomized.

The study design will be modified as follows:

- Part A: Evaluation of LY2157299 in Child-Pugh A or B7 patients with AFP $\geq 1.5x$ ULN. After stopping the 160-mg/day dose arm, all newly enrolled patients will be treated at the 300-mg/day dose.
- Part B: Evaluation of LY2157299 in Child-Pugh A or B7 patients with AFP <1.5x ULN

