5.1.10. Rationale for Amendment (e)

The protocol is being amended to add a Part E that will allow the evaluation of the safety and tolerability, pharmacokinetics and efficacy of LY2157299 administered according to a 21 days on/7 days off schedule.

Across the clinical development program at the time of Amendment (e), LY2157299 has shown a favorable short- and long-term toxicity profile in different studies and activity in different tumor types.

In light of cardiotoxicity observed in nonclinical trials of LY2157299, comprehensive cardiac safety monitoring was implemented in all clinical trials of LY2157299, including Study JBAK, and has been ongoing until the time of this amendment.

Using a data cut-off date of 15 September 2015, Lilly has performed a cross-study cardiovascular (CV) safety analysis of 745 patients from 10 completed and ongoing unblinded studies of LY2157299, including patients assigned to standard of care control arms who did not receive LY2157299. This analysis included a review of CV-related TEAEs and SAEs (with a focus on patients with increased valvular insufficiency and vascular-related hemorrhage/aneurysm, as well as patients with events of heart failure) and a correlation of TEAE/SAE data with central echocardiography findings, chest CT scan and/or MRI findings, cardiac laboratory markers (BNP, cystatin C, and troponin I) and central ECG findings. The cumulative results of this cross-study analysis did not identify any concerning trends in AEs, in particular those related to valvulopathies or aneurysms.

As described in Section 5.1.4, nonclinical toxicology data have determined a no-effect level for CV lesions that is higher than the observed and anticipated exposures in Study JBAK and other clinical trials. There is also no evidence of accumulation in patients given multiple doses of LY2157299 at 150 mg BID, suggesting that daily exposures on a schedule with increased days of dosing will remain lower than the no-effect-level for CV lesions characterized in toxicology studies.

In view of these clinical and nonclinical observations, Lilly has proposed and received endorsement from the United States (US) Food and Drug Administration to explore a new treatment schedule for LY2157299 in Part E of amended Study JBAK. This schedule will dose LY215729 at 150 mg twice daily for 21 days, followed by 7 days off drug (cycle length= 28 days). The goal is to improve upon the efficacy that has been observed in patients receiving

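### The 1.9-fold cardiac margin rests on a measured twice-daily AUC that is about half of what the protocol's own clearance implies

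*Protocol*

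**What the plan says.** Section 5.1.5.3 of the protocol lists a cardiac margin among the justifications for the study: "Clinical exposures achieved in Study JBAH are 1.9-fold below a no-observed-effect level for cardiac toxicity in the rat".

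The margin comes from Table JBAK.2 in Section 5.1.4.1. For total daily doses of 160 and 300 mg, the table gives two sets of steady-state AUC(0-24), in µg·h/mL:

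- measured, BID: 2.2 and 4.3
- simulated, QD: 4.1 and 7.7

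Against the rat no-observed-effect level (NOEL) for 3-month intermittent dosing (AUC 8.0), it prints margins of 3.6 and 1.9 on the BID row and 2.0 and 1.0 on the QD row. Footnote a gives the source of the QD row: "Simulations based on all clinical data from Study JBAH (Cohorts 1 to 5) assuming QD dosing". Section 5.1.5.3 attributes the 1.9 to Study JBAH as well, so both rows are tied to the same study.

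Section 5.1.3 describes the JBAH kinetics as a linear two-compartment model with an accumulation ratio of about 1. On clearance it says: "The mean population clearance of LY2157299 was 38.4 L/h with standard error", the standard error being 8%.

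Two later sections bear on the margin. Section 5.1.7 reports that in this study "patients administered 300 mg/day have higher exposures than previously observed for the same dose" level in JBAH. Section 5.1.10, in support of Part E, relies on a no-effect level for "CV lesions that is higher than the observed and anticipated exposures in Study JBAK" and other trials.

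**The concern.** In a linear system the 24-hour steady-state AUC depends on the total daily dose and clearance, not on whether the dose is given once or split in two. The two clinical rows of Table JBAK.2 should therefore be close. They differ by a factor of 1.8 to 1.9 at both doses, and the documents give no reason.

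The rationale text quotes only the margin from the row that disagrees with the reported clearance. The heart and great vessels are described in Section 5.1.4 as major target organs in animals. A margin of nearly 2 and a margin of about 1 against a cardiovascular no-effect level say different things to an ethics committee or an investigator. Section 5.1.10 then uses a no-effect-level argument for a schedule with more dosing days, and Section 5.1.7 says exposure at 300 mg/day was higher in this study than in JBAH.

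**Working it through.** **Inputs.** Measured BID AUCs 2.2 and 4.3, simulated QD AUCs 4.1 and 7.7, and rat NOEL AUC 8.0 (Table JBAK.2). Clearance 38.4 L/h with 8% standard error, and 46% between-patient variability on apparent clearance (Section 5.1.3).

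**Step 1: reproduce the stated figure.** Margin = NOEL AUC / clinical AUC. At 300 mg/day BID, 8.0/4.3 = 1.86, printed as 1.9. The other printed ratios, 16 in all, also follow from the printed AUCs. There is no division error.

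**Step 2: AUC implied by the reported clearance.** AUC(0-24) = daily dose / clearance; mg·h/L equals µg·h/mL.

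| | 160 mg/day | 300 mg/day |
|---|---|---|
| Daily dose / 38.4 | 4.17 | 7.81 |
| Simulated QD row | 4.1 (98%) | 7.7 (99%) |
| Measured BID row | 2.2 (53%) | 4.3 (55%) |
| QD row / BID row | 1.86 | 1.79 |
| Clearance implied by BID row | 160/2.2 = 72.7 L/h | 300/4.3 = 69.8 L/h |
| One BID dose / 38.4 | 80/38.4 = 2.08 | 150/38.4 = 3.91 |

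Rounding of the printed AUCs does not close the gap: the QD/BID ratio lies between 1.80 and 1.93 at 160 mg/day and between 1.76 and 1.82 at 300 mg/day. The measured values lie close to the AUC of a single dose.

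**Step 3: effect on the margin.** Using daily dose over clearance against the NOEL AUC of 8.0:

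- 300 mg/day: 8.0/7.81 = 1.02, against the printed 1.9. With clearance at ±1.96 standard errors (32.4 to 44.4 L/h) the range is 0.86 to 1.18.
- 160 mg/day: 8.0/4.17 = 1.92, against the printed 3.6.
- For context, the multiple to the rat lowest-observed-effect level at 300 mg/day is 24.2/7.81 = 3.1, against the printed 5.6.

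**Step 4: could sampling error explain it?** Assume log-normal clearance, so the log-SD is √ln(1 + 0.46²) = 0.438. The documents do not give cohort sizes, so n per dose is an assumption, shown from 3 to 10. Combined SE = √(0.08² + 0.438²/n), which is 0.265 at n = 3 and 0.160 at n = 10. The log gaps are ln(7.81/4.3) = 0.597 and ln(4.17/2.2) = 0.639. The gap is therefore about 2.3 to 3.7 SE at 300 mg/day and 2.4 to 4.0 SE at 160 mg/day. Chance is an unlikely explanation, but how unlikely depends on cohort sizes that are not reported.

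**Step 5: a supporting check only.** Section 5.1.3 reports a 2.04-fold AUC increase per doubling of dose (90% limits 1.43 to 2.89). Moving from BID to QD at the same daily dose doubles each dose and halves the number of doses, so the expected ratio is 2.04/2 = 1.02 (0.72 to 1.45). Both table ratios exceed 1.45. The reported comparison spans 20 to 150 mg BID, so applying it to a single 300 mg dose is an extrapolation.

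**The case against.** The strongest reply is that nothing is miscalculated and nothing is hidden. The 1.9 follows from the table, and the table prints the 1.0 for simulated QD beside it, labelled by method. Its note says shading marks the relevant margin, though the shading is not visible in the public text. The Investigator's Brochure, to which the protocol refers for detail, might define the AUC interval. All of that stands, but none of it explains in the protocol why the two rows differ.

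The close agreement between the QD row and daily dose over clearance is also nearly circular. Both derive from JBAH Cohorts 1 to 5, and a linear model returns dose over clearance by construction. The agreement does not prove the QD row right. The non-compartmental clearance that could test the measured row is not reported. This stands too, and is why the point is an inconsistency rather than a finding against one row.

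Four stronger readings are tempting and are not supported:

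- A reader might infer that the true margin is 1.0. That holds only if the reported clearance is right and the measured AUCs are not.
- A reader might infer that the measured values are single-dose AUCs. The numbers fit, but the documents do not say how the JBAH AUCs were derived. Omitting the evening dose before the Day 15 sample is described as a rule of this study, not of JBAH.
- A reader might infer that Section 5.1.10 is false. It does not name its NOEL. Table JBAK.2 also lists 30-day values of 36.3 and 23.9, and 7.81 is nominally below even 8.0. It is unconfirmed, not contradicted.
- A reader might infer that the male-rat basis of the 8.0 flatters the margin. Footnote c discloses it: "AUC from males were used to calculate MOS or exposure multiple to the LOEL". If females had higher exposure at a dose without effects, as the 28-dose study in Section 5.1.1 suggests, the male value gives the smaller margin.

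Finally, separate clinical cardiac evidence supports the programme, including a 745-patient cross-study review in Section 5.1.10. Section 5.1.7 accepted higher exposure on clinical safety and benefit-risk grounds. This limits the consequence but does not make the 1.9 supported.

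**Conclusion.** The inconsistency holds. On the protocol's own linear kinetics and clearance, the measured BID AUCs are 53% to 55% of the expected 24-hour exposure, and the 1.9-fold margin would be about 1.0. Confidence is high that the table and Section 5.1.3 do not agree as written; there is no basis for saying which is wrong. The conclusion rests on linearity, on 38.4 L/h being the apparent oral clearance, and on both rows describing JBAH patients.

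The reach is limited. No endpoint, analysis or monitoring rule uses 1.9, and the pharmacokinetic criterion at the first interim analysis in Section 12.2.14 has its own AUC threshold (10.96 mg·h/L). The affected text is the safety rationale in Sections 5.1.4.1 and 5.1.5.3. Section 5.1.10 needs a check: if its comparator is the 8.0 and the clearance-based 7.81 is right, an exposure only 2.4% higher (8.0/7.81 = 1.024) would reach that level, and Section 5.1.7 reports higher exposure without giving a figure.

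**What to change.** Reconcile Sections 5.1.3, 5.1.4.1 and 5.1.5.3 by stating, under Table JBAK.2, the time interval and the number of doses that the measured BID AUC covers.

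- If it is not a full 24-hour BID exposure, correct the BID margins in the table and the 1.9-fold statement.
- If it is, explain why it is roughly half of daily dose over clearance.

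Then confirm that the no-effect-level statement in Section 5.1.10 holds against the reconciled exposures and against the higher exposures reported in Section 5.1.7, and name the NOEL it refers to. No dose or schedule is proposed here.

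The cost is a recalculation from existing JBAH data, wording changes in Sections 5.1.4.1 and 5.1.5.3, and a check of Section 5.1.10. The stated margin may become less favourable.
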